### ***Malignancies***

The impact of immunosuppression on the development of malignancies is not known, however an increased rate of some malignancies, notably lymphoma, has been observed in RA patients. Although no imbalance of malignancies was observed in clinical trials of Clazakizumab, malignancies have been identified as a concern for other biologics. It is recognized that identification of such events in clazakizumab-treated patients may require a longer period of surveillance. Clazakizumab should be discontinued in patients with malignancies (with the exception of local basal or squamous cell carcinoma of the skin that is completely excised with free margins).

### ***Demyelinating Disorders***

The impact of treatment with clazakizumab on demyelinating disorders is not known; events were rarely reported. Patients should be closely monitored for signs and symptoms potentially indicative of central demyelinating disorders. Physicians should exercise caution in considering the use of clazakizumab in patients with pre-existing or recent onset demyelinating disorders. Treatment with clazakizumab should be interrupted during

assessment of a potential demyelination event and only resumed if the benefit of continuing study drug is favorable.

### ***Hypersensitivity or Anaphylaxis***

An infusion/dose reaction is defined as an adverse event occurring during and within 24 hours after the infusion or SC injection of clazakizumab. This may include hypersensitivity reactions or anaphylactic reactions.

Signs of a possible hypersensitivity reaction include but are not limited to:

- fever, chills, pruritus, urticaria, angioedema, and skin rash.
- cardiopulmonary reactions, including chest pain, dyspnea, hypotension or hypertension.

Healthcare professionals administering clazakizumab should be trained in the appropriate administrative procedures, be able to recognize the symptoms associated with potential anaphylactic or hypersensitivity reactions, and have the appropriate medication available for immediate use in case of anaphylaxis or hypersensitivity reaction during or after administration of clazakizumab. Healthcare professionals should also instruct patients to seek medical attention if they experience symptoms of a hypersensitivity reaction outside of the clinic.

If a patient has symptoms of anaphylaxis or serious hypersensitivity, or requires an interruption of the study drug because of symptoms of anaphylaxis or hypersensitivity, administration of clazakizumab must be discontinued permanently. The patient should be treated according to the standard of care for management of the hypersensitivity reaction. A blood sample for the presence of anti-clazakizumab antibodies should be obtained.

Clazakizumab should not be administered to subjects who have had any previous allergic reactions to monoclonal antibodies. To date, no infusion reactions have been associated with clazakizumab administered by IV infusion. Injection site reactions have been reported with SC administration. Reactions have been mild or moderate and have resolved without treatment. Both allergic reactions and injection site reactions should be treated with standard of care. Subjects who have developed significant allergic reaction to study drugs should not be re-challenged.

### ***Viral Reactivation***

Though rarely reported within the clazakizumab program due to exclusion criteria at study entry, reactivation of viral and other serious infections (e.g. EBV or TB) has been observed with biologic therapies.

### ***Drug Interaction***

The formation of CYP450 enzymes may be suppressed by increased levels of cytokines (eg, IL-6) during chronic inflammation. Therefore, it is expected that for molecules that antagonize cytokine activity, such as clazakizumab, the formation of CYP450 enzymes could be normalized. When starting or stopping therapy with clazakizumab, patients taking medications which are individually dose-adjusted and metabolized via CYP450, 3A4, 1A2, or 2C9 (e.g. atorvastatin, calcium channel blockers, theophylline, warfarin, phenytoin, cyclosporine, or benzodiazepines) should be monitored as doses may need to be adjusted to maintain their therapeutic effect. Given its long elimination half-life ( $t_{1/2}$ ), the effect of clazakizumab on CYP450 enzyme activity may persist for several weeks after stopping therapy.

### ***Pregnancies and Women of Child Bearing Potential***

There are no adequate well-controlled studies in pregnant or lactating women. In nonclinical studies, an increase in the number of monkeys with retention of the placenta at parturition was observed at clazakizumab doses corresponding to 22 and 220 times the planned human dose of 25 mg. In 3 of the 5 monkeys with retained placentas, the resulting excessive uterine hemorrhage led to moribund status in the mothers.

Three pregnancies have been reported to date in subjects taking clazakizumab. The outcomes included one spontaneous abortion (outcome unknown for the other 2 pregnancies).

All subjects of child bearing potential being treated with clazakizumab (and their partners) must be informed of this risk, and use highly effective birth control, as defined in the study protocol. Administration of clazakizumab may decrease the efficacy of hormonal oral contraceptive.

Under no circumstances shall clazakizumab injection be administered to women known to be pregnant or lactating. All pregnancies must be reported to Vitaeris within 24 hours and in accordance with SAE reporting procedures.

## **Pantoprazole**

The most common reported **side effects of pantoprazole** are headache, diarrhea and injection site thrombophlebitis. Other common side effects are rash, tiredness, flu-like symptoms, nausea, vomiting, abdominal pain/discomfort, constipation, dry mouth, loose stools, and flatulence. While some patients show increases in liver enzymes, hepatic failure is very rare. Rare events are fever, taste disorders, gynecomastia, agranulocytosis, thrombocytopenia, severe skin reactions or allergic reactions. Occurrence of interstitial nephritis is very rare.

## **10. SAFETY ASSESSMENT AND REPORTING**

### **Definition of adverse events**

An AE is any untoward adverse change from the subject's baseline condition, i.e., any unfavorable and unintended sign including an abnormal laboratory finding, symptom or disease which is considered to be clinically relevant by the physician that occurs during the course of the study, whether or not considered related to the study drug.

Adverse events include:

- Exacerbation of a pre-existing disease.
- Increase in frequency or intensity of a pre-existing episodic disease or medical condition.
- Disease or medical condition detected or diagnosed after study drug administration even though it may have been present prior to the start of the study.
- Continuous persistent disease or symptoms present at baseline that worsen following the start of the study.
- Lack of efficacy in the acute treatment of a life-threatening disease.
- Events considered by the investigator to be related to study-mandated procedures.
- Abnormal assessments, e.g., ECG and physical examination findings, must be reported as AEs if they represent a clinically significant finding that was not present at baseline or worsened during the course of the study.
- Laboratory test abnormalities must be reported as AEs if they represent a clinically significant finding, symptomatic or not, which was not present at baseline or worsened during the course of the study or led to dose reduction, interruption or permanent discontinuation of study drug.

Adverse events do not include:

- Pre-planned interventions or occurrence of endpoints specified in the study protocol are not considered AE's, if not defined otherwise (eg.as a result of overdose)
- Medical or surgical procedure, e.g., surgery, endoscopy, tooth extraction, transfusion. However, the event leading to the procedure is an AE. If this event is serious, the procedure will be described in the SAE narrative.
- Pre-existing disease or medical condition that does not worsen.
- Situations in which an adverse change did not occur, e.g., hospitalizations for cosmetic elective surgery or for social and/or convenience reasons.
- Overdose of either study drug or concomitant medication without any signs or symptoms. However, overdose must be mentioned in the Study Drug Log.

### **Serious Adverse Events (SAEs)**

A Serious Adverse Event (SAE) will be defined by the International Conference on Harmonization (ICH) guidelines and WHO GCP guidelines as any AE fulfilling at least one of the following criteria:

- Results in deaths.
- Life-threatening – defined as an event in which the subject was, in the judgment of the investigator, at risk of death at the time of the event; it does not refer to an event that hypothetically might have caused death had it been more severe.
- Requiring subject's hospitalization or prolongation of existing hospitalization – inpatient hospitalization refers to any inpatient admission, regardless of length of stay.
- Resulting in persistent or significant disability or incapacity (i.e., a substantial disruption of a person's ability to conduct normal life functions).
- Congenital anomaly or birth defect.
- Is medically significant or requires intervention to prevent at least one of the outcomes listed above.

Life-threatening refers to an event in which the subject was at risk of death at the time of the event. It does not refer to an event that hypothetically might have caused death if it were more severe. Important medical events that may not immediately result in death, be life-threatening, or require hospitalization may be considered as SAEs when, based upon appropriate medical judgment, they may jeopardize the subject and may require medical or surgical intervention to prevent one of the outcomes listed in the definitions above.

### **Hospitalization – Prolongation of existing hospitalization**

Hospitalization is defined as an overnight stay in a hospital unit and/or emergency room. An additional overnight stay defines a prolongation of existing hospitalization.

The following is not considered an SAE and will be reported as an AE only:

- Treatment on an emergency or outsubject basis for an event not fulfilling the definition of seriousness given above and not resulting in hospitalization.

The following reasons for hospitalizations are not considered AEs, and therefore not SAEs:

- Hospitalizations for cosmetic elective surgery, social and/or convenience reasons.
- Standard monitoring of a pre-existing disease or medical condition that did not worsen, e.g., hospitalization for coronary angiography in a subject with stable angina pectoris.
- Elective treatment of a pre-existing disease or medical condition that did not worsen, e.g., hospitalization for chemotherapy for cancer, elective hip replacement for arthritis.

#### *SAEs related to study-mandated procedures*

Such SAEs are defined as SAEs that appear to have a reasonable possibility of causal relationship (i.e., a relationship cannot be ruled out) to study-mandated procedures (excluding administration of study drug) such as discontinuation of subject's previous treatment during a washout period, or complication of a mandated invasive procedure (e.g., blood sampling, heart catheterization), or car accident on the way to the hospital for a study visit, etc.

#### *Suspected unexpected serious adverse reactions (SUSARs)*

SUSARs are all serious adverse reactions with suspect causal relationship to the study drug that is unexpected (not previously described in the Investigator's brochure) and serious.

#### **Pregnancy**

Pregnancy itself is not an AE/SAE; the outcome of a pregnancy can be a SAE. Any pregnancy that occurs during study participation will be reported to the investigator/sponsor. To ensure subject safety, each pregnancy will be reported to the investigator/sponsor immediately. The pregnancy will be followed up to determine outcome (including premature termination) and status of mother and child. Pregnancy complications and elective terminations for medical reasons will be reported as an AE or SAE. Spontaneous abortions will be reported as an SAE. Any SAE occurring in association with a pregnancy brought to the investigator's attention after the subject has completed the study and considered by the investigator as possibly related to the investigational product, will be promptly reported to the principal investigator/sponsor. In addition, the investigator will attempt to collect pregnancy

information on any female partners of male study subjects who become pregnant while the subject is enrolled in the study. Pregnancy information will be reported to the investigator/sponsor as described above.

### **Severity of adverse events**

The severity of clinical AEs will be graded on a three-point scale: mild, moderate, severe, and reported on specific AE pages of the CRF. If the severity of an AE worsens during study drug administration, only the worst intensity should be reported on the AE page. If the AE lessens in intensity, no change in the severity is required. If an AE occurs during a washout or placebo run-in phase and afterwards worsens during the treatment phase, a new AE page will be filled in with the intensity observed during study drug administration.

**Mild:** Event may be noticeable to subject; does not influence daily activities; the AE resolves spontaneously or may require minimal therapeutic intervention;

**Moderate:** Event may make subject uncomfortable; performance of daily activities may be influenced; intervention may be needed; the AE produces no sequelae.

**Severe:** Event may cause noticeable discomfort; usually interferes with daily activities; subject may not be able to continue in the study; the AE produces sequelae, which require prolonged therapeutic intervention.

A mild, moderate or severe AE may or may not be serious. These terms are used to describe the intensity of a specific event (as in mild, moderate, or severe myocardial infarction). However, a severe event may be of relatively minor medical significance (such as severe headache) and is not necessarily serious. For example, nausea lasting several hours may be rated as severe, but may not be clinically serious. Fever of 39°C that is not considered severe may become serious if it prolongs hospital discharge by a day. Seriousness rather than severity serves as a guide for defining regulatory reporting obligations.

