## **3. STUDY DESIGN**

This bi-center study (MUW, Charité Berlin) is an investigator-driven pilot trial designed to assess the safety, tolerability, pharmacokinetics, pharmacodynamics and efficacy (preliminary assessment) of humanized anti-IL-6 monoclonal antibody clazakizumab in kidney transplant recipients with late ABMR. This study, a phase 2 trial, has two subsequent sub-parts, a randomized placebo-controlled trial (part A) of 12 weeks, where recipients are allocated to receive either clazakizumab (n=10) or placebo (n=10), followed by an open-label prospective study, where all 20 study patients will receive clazakizumab for a period of 40

weeks. In this second part, treatment will be offered to all subjects for two major reasons: (i) in a recent uncontrolled preliminary observational study, interference with IL-6/IL-6R blockade in ABMR patients using tocilizumab was reported to be safe and well tolerated, and first results have suggested stabilization of kidney function in many of the treated patients; (ii) two subsequent protocol biopsies planned in our trial, which are necessary for an in-depth analysis of the early and late effects of IL-6 blockade, would not be justified for long-term placebo treatment. After completion of part A, the randomization sequence will be unblinded for a first analysis of data. A simplified flow chart of the trial is shown in Figure 1:

Figure 1. Trial overview

**Part A:** Patients will be randomized to receive either clazakizumab (25 mg subcutaneous [SC] administration) or placebo (1:1 randomization) for a period of 12 weeks (administration of clazakizumab/placebo at day 0, and after 4 and 8 weeks). After 12 weeks, patients will be subjected to a first follow-up biopsy. Primary goals of this part of the trial are to assess the safety, pharmacokinetics and pharmacodynamics of a short course of treatment. Moreover, part A will allow for a first preliminary assessment of the impact of clazakizumab on ABMR-associated inflammation detected in peripheral blood and in the rejecting organ allograft, on the pharmacokinetics of pantoprazole as a probe drug to investigate influence of IL-6 blockade on cytochrome P450-dependent drug metabolism, and on the short-term course of DSA MFI and kidney allograft function (eGFR, urinary protein excretion). The randomization

sequence will be unblinded for a first data analysis after the last patient has completed the 12-week follow-up period.

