**Part B:** After 12 weeks, all study patients will enter an open-label part of the study. All 20 subjects will receive clazakizumab (25 mg SC injection) in 4-weekly intervals until the end-of-study (EOS) visit after 52 weeks and will then be subjected to a second protocol biopsy. Major goals of part B are to evaluate the safety and tolerability of a prolonged period of treatment with clazakizumab and the long-term impact of this antibody on the evolution of ABMR, rejection-associated biomarkers and kidney allograft function and survival over a period of 12 months.

We expect a recruitment phase of 18 months, and thus completion of the trial after 30 months.

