### **Blinding and unblinding**

The first part (A) of the study is designed as a double-blinded trial, in order to minimize bias. Investigational drug (clazakizumab) and placebo (normal 0.9% saline) are prepared by non-blinded pharmacists and formulated to have identical appearance. Neither study participants nor medical staff interacting with patients or data know the assigned treatment (clazakizumab versus placebo). The randomization sequence will be unblinded after the last patient has completed the 12-week follow-up period. Premature unblinding may be necessary in cases of medical emergencies or serious medical conditions, where participants cannot be treated adequately unless the medical staff knows the allocated treatment. Unblinding can, if necessary, be requested by the DSMB.

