## 8. INTERIM ANALYSES

This study will be monitored by an independent data and safety monitoring board (DSMB) to assess the safety and data quality. To timely detect major differences between groups in terms of safety aspects, the board members will be instructed to perform interim analyses after 10 and 20 patients have finalized part A of the study. The DSMB will analyze recorded AEs and safety lab results in relation to the randomization sequence. The trial will be terminated prematurely in the following cases: (i) if adverse events occur which are so serious that the risk-benefit ratio is not acceptable, and (ii) if the number of dropouts is so high that proper completion of the trial cannot realistically be expected. For this pilot trial, exact statistical definitions of criteria for premature study termination are not defined.

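### The AE severity rule makes no provision for the week-12 switch, so a grade reached on open-label clazakizumab can sit on an AE page that starts in part A

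*Combined protocol and SAP*

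**What the plan says.** Section 10, under Severity of adverse events, gives two recording rules.

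- General rule: "If the severity of an AE worsens during study drug administration, only the worst intensity should be reported on the AE page". If the event eases, the grade need not change, so the page holds the worst grade over the life of the event.
- Exception: "If an AE occurs during a washout or placebo run-in phase and afterwards worsens during the treatment phase, a new AE page will be filled". That page takes the intensity seen on study drug.

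Section 10, under Reporting procedures, lists the details to be entered for each AE. They include one start, one end, one severity grade and one serious yes/no item. A date of worsening and the study part are not listed.

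Section 3 describes part A as 12 weeks of randomised, double-blind treatment with 10 patients per arm. Then: "After 12 weeks, all study patients will enter an open-label part of the study". Section 4 uses the term study drug for clazakizumab and placebo injections alike. On timing, Blinding and unblinding states: "The randomization sequence will be unblinded after the last patient has completed the 12-week follow-up period". Section 8 adds interim looks after 10 and 20 patients have finished part A: "The DSMB will analyze recorded AEs and safety lab results in relation to the randomization sequence".

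Section 7 plans Fisher's exact test for the occurrence of AEs by arm in part A, and Kaplan-Meier and log-rank analysis of survival free of AEs or SAEs.

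**The concern.** Safety and tolerability are the primary outcome, and part A is the only placebo-controlled look at them. That comparison needs each event's part A severity to be what was seen before the open-label injections began. The plan has a rule that separates placebo-phase events from later worsening on drug, but it is written for phases that this trial does not have. The switch that does occur is left to the general rule, which keeps one worst grade per event.

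Two things are at stake. Part A severity summaries, and the DSMB's by-arm review of recorded AEs, can include grades reached in part B. And for a patient moved from placebo to clazakizumab, a worsening soon after first exposure need not appear as a part B record at all, although it is a signal that the open-label part should show.

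**Working it through.** **Step 1: which rule applies at week 12.** The exception needs a washout phase or a placebo run-in. Section 3 describes neither: the placebo period is a randomised arm. A generous reading that treats the placebo arm as a run-in would be hard to apply, because the allocation is not released until the last patient reaches week 12, so staff would not know for whom to use it. Section 4 counts both products as study drug, so the general rule is the one whose words fit a worsening after week 12.

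**Step 2: what the record then holds.** Take an AE that starts at week 10, is mild at week 12 and becomes severe at week 20. Under the general rule there is one page, with start week 10 and grade severe. The listed items do not show that the severe grade was reached in part B. The same happens in a patient randomised to clazakizumab.

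**Step 3: which analyses are exposed.**
- Occurrence of AEs in part A (Fisher's exact test): not exposed. An AE that began in part A counts once whatever its grade.
- Severity summaries of part A and the DSMB's review by arm: exposed.
- SAE-free survival: exposed only if a serious flag set in part B is dated to the onset of the AE. The documents do not say how it is dated.

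**Step 4: how much part B time has passed at each look.** Assumption: 20 patients enrolled at equal intervals over the stated 18 months (78 weeks), spacing 78/19 = 4.105 weeks. A patient enrolled at week t enters part B at t + 12. The last patient reaches week 12 at 78 + 12 = 90. Part B time is then min(40, 78 − t).
- Ten patients have 78 − t of at least 10 × 4.105 = 41.1 weeks, so they are at the 40-week cap.
- The other ten have 0, 1, …, 9 times 4.105 weeks; the sum is 45 × 4.105 = 184.7.
- Mean = (10 × 40 + 184.7)/20 = 29.2 weeks, about 6.7 months. Nineteen of 20 have some part B time.
- At the first DSMB look, when the tenth patient finishes part A, the first ten have 0 to 9 times 4.105 weeks. Mean = 184.7/10 = 18.5 weeks, about 4.3 months.

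This is the time in which grades can change. It is not a count of affected events.

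**Step 5: sensitivity with 10 per arm.** One patient is 1/10 = 10 percentage points. As an illustration with assumed numbers of patients with a severe AE (the plan names no such test), two-sided Fisher p-values are:

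| Clazakizumab v placebo | p |
|---|---|
| 5/10 v 0/10 (true part A grades) | 0.033 |
| 5/10 v 1/10 (one placebo patient carries back a part B grade) | 0.141 |
| 6/10 v 0/10 (one clazakizumab patient does) | 0.011 |
| 6/10 v 1/10 (one in each arm) | 0.057 |

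One affected patient changes the picture noticeably, and the direction depends on the arm.

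**The case against.** The strongest case against has five parts.

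1. **Attribution is not stated.** No section assigns an AE to an arm or study part by its start date. A reader might infer that a placebo patient's event will be recorded as a worse placebo event. The text does not establish that; it leaves the case unregulated. This stands, and the point is limited to what can happen.
2. **Seriousness is separate.** The worst-intensity rule concerns severity, and the same subsection distinguishes severity from seriousness. An SAE also gets a written report with a description of the event, and follow-up where applicable. So it does not follow that a serious worsening in part B leaves no trace. This stands. What remains is the single serious item on the AE page and its undefined date.
3. **Direction.** A reader might infer that the errors favour the drug. The rule works in both arms: an AE that starts on clazakizumab in part A and worsens in part B inflates the clazakizumab arm. Table 5 shows more AEs on 25 mg than on placebo (84.7% v 60.7% and 73.2% v 65.9%), so that arm could have more events open to regrading. This stands; the net direction is unknown.
4. **The CRF is not in the documents.** It may hold dated grade changes or completion guidance, and injection dates are recorded. This stands in part: dates could be recovered from source, but the protocol asks for no date of worsening.
5. **Staff could open a new page for everyone at week 12 without knowing the allocation.** True, and the fix uses this. But nothing in the protocol tells them to.

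**Conclusion.** The concern holds in a limited form. The new-page rule refers to phases that the trial does not have, and the rule that does apply can put a part B grade on an AE that began in part A, in either arm. Severity summaries of part A and the DSMB's by-arm review can be contaminated. SAE-free survival can be affected only if a later serious flag is dated to AE onset. Worsening after first exposure in switched patients can be hidden.

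The documents do not support a claim that the planned part A test of AE occurrence is wrong, or that the part A contrast is biased in the drug's favour.

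The size is bounded only loosely. Affected events are AEs still ongoing at week 12 that later worsen, and their frequency cannot be estimated from the documents. The exposure figures (mean 29.2 weeks of part B at the end of part A, 18.5 weeks at the first DSMB look) rest on even enrolment over 18 months, no dropout, and AE pages being read as they stand on those dates. The change is worth making because safety is the primary outcome, the arms are small and the cost is low.

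**What to change.** In Section 10, Severity of adverse events, replace the sentence on washout and run-in with a rule for both arms, for example:

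*For every AE ongoing at week 12, severity and seriousness are recorded before the first open-label injection and are final for part A. Any later worsening is entered as a part B record with its own date, linked to the part A event.*

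The linked record can be a new AE page or a dated grade-change field. Add the date and the study part to the list of AE details under Reporting procedures.

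In Sections 7 and 8, state that part A tables, including those for the DSMB, use only severity and seriousness up to the first open-label injection, and that linked records are not counted as separate events in 52-week totals. The last clause matters because a new page would otherwise count one continuing event twice, including in patients who never changed treatment.

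Cost: a short protocol change, a CRF completion rule and a few extra linked records. Week 12 already has AE monitoring in the schedule of events. Because the rule is the same in both arms, it does not touch the blind.
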